8.5 Extent of exposure

Study drug summary and compliance summaries will be based on the safety population. Drug administration details including derived variables will be provided in the form listings in addition to the below summaries.

8.5.1 Treatment duration

The duration of treatment will be derived using the dates of first/last study drug administration from the patient diary as date of last dose – date of first dose + 1.

Duration of treatment (days) and duration of study (days) will be summarised based on the safety population using descriptive statistics. Refer to [section 7.1](#) for the derivation of variables. In addition, descriptive summary will be provided for total number of doses taken (based on the patient daily dosing diary). This will also be presented in categories “1-7, 8-14, 15-21, 22-28, 29-35, 36-42, 43-49, 50-56, 57-63, 64-70, 71-77, 78-84” using count and

Statistical Analysis Plan (SAP)

percentage.

Total number of missed doses collected from patient daily dosing diary presented in categories 0, 1, ≥ 2 using count and percentage.

8.5.2 Treatment compliance

Compliance will be calculated in 2 different ways: based on the patient daily dosing diary and using drug accountability records.

Study drug compliance based on the number of tablets taken will be calculated as: $[(\text{Total number of tablet dispensed across all visits} - \text{Total number of tablet returned across all visits}) / \text{Duration of study drug (days)}] \times 100$.

Study drug compliance based on the patient daily dosing diary will be calculated as: $[(\text{Total number of tablet taken as per daily dosing dairy}) / \text{Duration of treatment}] \times 100$.

Study drug compliance (based on the patient daily dosing diary and using drug accountability records) will be summarized. Compliance will also be summarized in categories <80%, 80% - 120%, >120% using frequency tables.

Study drug compliance summaries will be based on the safety population.

8.5.3 Exposure to CR845

The exposure to CR845 (mg) will be calculated also using the patient daily dosing diary, however, the actual dose levels taken by the patient will be taken into account rather than the number of tablets (i.e. for a correctly dosed placebo patient, exposure to CR845 = 0mg).

8.6 Efficacy analyses

This section describes the analysis to be conducted on the primary, secondary and additional efficacy variables. All the efficacy analyses will be performed using the full analysis set and data that is collected on or prior to the date of treatment discontinuation/completion. An analysis of the primary and secondary efficacy variables for the per-protocol population will be performed if more than 20% of the FAS patients are excluded in any of the treatment groups. Each CR845 dose group, will be compared against placebo for all the endpoints. In addition, a separate analysis comparing all CR845 doses pooled against placebo will be performed with respect to the primary and key secondary variables. Only the results for the all CR845 doses pooled group and the comparison with placebo will be presented from these analyses. An analysis of all CR845 doses pooled versus placebo with respect to the rest of the secondary variables may also be considered. A dose response analysis will be performed with respect to the primary and key secondary variables. Results for the primary and secondary efficacy variables will be presented by renal disease status (moderate CKD non-dialysis; severe CKD non-dialysis; severe CKD on dialysis).

Statistical Analysis Plan (SAP)

8.6.1 Analysis methods

8.6.1.1 Multiplicity

There will be no adjustment for multiple comparisons.

8.6.1.2 Treatment by center interaction analysis (multi-center study)

Given the large (~60) number of sites with few patients per site, no analysis will be conducted to assess the treatment-by-center interaction.

8.6.2 Analysis of primary efficacy endpoint

The primary efficacy endpoint is defined as the change from baseline to week 12 of the Treatment period with respect to the weekly mean of the daily 24 hour Worst Itching Intensity NRS score. Testing of the primary efficacy endpoint will be 2-sided and conducted at the 5% error level.

The study will be considered positive if at least one safe and efficacious dose is identified. Effectiveness will be evaluated based on results of the primary efficacy analysis either using the estimate of treatment effect or the p-value of the hypothesis tests.

The null hypotheses H_{01} , H_{02} , H_{03} , and H_{04} given below will be tested against the alternative hypotheses H_{A1} , H_{A2} and H_{A3} respectively:

$$\begin{array}{llll} H_{01}: \mu_{D1} - \mu_P = 0, & H_{02}: \mu_{D2} - \mu_P = 0, & H_{03}: \mu_{D3} - \mu_P = 0, & H_{04}: \mu_{D123} - \mu_P = 0 \\ H_{A1}: \mu_{D1} - \mu_P \neq 0, & H_{A2}: \mu_{D2} - \mu_P \neq 0, & H_{A3}: \mu_{D3} - \mu_P \neq 0, & H_{A4}: \mu_{D123} - \mu_P \neq 0 \end{array}$$

Where μ_{D1} , μ_{D2} and μ_{D3} denote the mean change in Worst Itching Intensity NRS score from baseline to week 12 in the three active treatment dose groups and μ_P denotes the mean change from baseline to week 12 in the placebo group (placebo, P). D_1 denotes the CR845 0.25mg dose group, D_2 denotes the CR845 0.5mg dose group and D_3 denotes the CR845 1mg dose group and D_{123} denotes the doses (0.25, 0.5 and 1 mg) combined.

The weekly mean of the 24-hour Worst Itching Intensity NRS score will be defined as the sum of the daily Worst Itching Intensity NRS score reported during a specific week of the Treatment period (eg, Days 1 to 7, Days 8 to 14, Days 15 to 21, etc. till 78 to 84) divided by the number of non-missing scores for that week. If there are <4 non-missing daily worst itching scores during a specific week, the corresponding weekly mean worst itching score will be set to missing. The baseline score will be defined as the average of the daily 24-hour Worst Itching Intensity NRS scores over the last 7 days prior to randomization; at least 4 completed Worst Itching Intensity NRS worksheets will be required prior to randomization.

The primary efficacy variable will be analyzed using a mixed effects model with repeated measures (MMRM). The model will contain treatment, week, and treatment-by-week interaction as fixed effects; baseline score and renal disease status as covariates. For each

Statistical Analysis Plan (SAP)

dose group, the treatment group difference vs placebo will be estimated as the simple contrast in the treatment effect at Week 12 of the Treatment Period. The treatment difference between all doses combined and placebo will be estimated using a similar approach.

For week 12, the adjusted least square means (LS means) and standard error (SE) from the model will be presented for each treatment group. The LS means estimate for the difference, standard error, 95% CI, and p-value will also be presented. The primary analysis will be conducted using the Full Analysis Set. A summary table including descriptive statistics (n, mean, SD, median, minimum, maximum) for the observed value and the change from baseline by treatment group will also be provided for the NRS score.

An unstructured covariance matrix structure will be used to model the within patient errors. If there are convergence issues, other structures that require fewer parameters will be applied in the following order: 1) heterogeneous Toeplitz, 2) autoregressive, 3) compound symmetry until convergence is attained. The Kenward-Roger approximation will be used to estimate the denominator degrees of freedom.

For the MMRM analyses, the missing Weekly NRS score will be imputed using a Multiple Imputation (MI) approach, assuming that patients who discontinue study drug early would have similar Worst Itching Intensity NRS scores as other patients in their respective treatment arm that have complete data. The details of missing data imputations described as below.

- Intermittent missing weekly NRS scores will first be imputed using the Markov Chain Monte Carlo (MCMC) method implemented with the SAS MI procedure, which is appropriate for non-monotonic missing data. Additional terms for baseline NRS score and randomization stratification category (as dummy 0/1 variables) will be added. This will be performed within each treatment group separately.
- The monotone missing weekly NRS values will then be multiply imputed with the SAS MI procedure using the monotone regression method. The regression model will include terms for treatment group, baseline NRS score, and randomization stratification category; all previous non-missing post-baseline NRS scores will be included in the model. Should convergence issues occur due to small cell size for the categorical covariates at either stage, they will be removed from the model.
- The change from baseline at Week 12 with respect to the weekly mean of the daily 24-hour Worst Itching Intensity will be analyzed for each imputed dataset using an MMRM model.
- One hundred imputations will be performed.

Statistical Analysis Plan (SAP)

- Results of the MMRM analysis on the multiply imputed data sets will be summarized by the SAS MIANALYZE procedure.

The details of MI SAS procedure described in [Appendix F](#).

In addition, sensitivity analyses of the primary efficacy endpoint will be conducted to evaluate the robustness of study results under different assumptions and imputation algorithms, as described below:

Sensitivity analysis 1 (No imputation; Missing at Random [MAR]):

In this sensitivity analysis, missing weekly worst itching scores will not be imputed. Assuming the data are MAR, the estimates of the treatment differences calculated from the MMRM model described above are unbiased. Details of analysis using SAS described under [Appendix G](#).

Sensitivity analysis 2 (Multiple Imputation; Missing Not at random (MNAR))

This sensitivity analysis is an implementation of a pattern mixture model that draws from different populations based on the reason for withdrawal.

- Intermittent missing NRS scores will first be imputed using the MCMC method with the SAS MI procedure, which is appropriate for non-monotonic missing data. This will be performed within each treatment group separately.
- For patients who discontinue study drug due to adverse events, data missing after discontinuation will be imputed using the distribution of the baseline value of all patients' weekly worst itching score with the same renal status assuming a trimmed normal (from 5 to 10).
- For patients who discontinue study drug due to reasons other than adverse event, monotone missing weekly NRS values will be multiply imputed with the SAS MI procedure using the monotone regression method applied to all patients with data available at the particular visit (including those withdrawing due to an adverse event). The regression model will include terms for treatment group, baseline NRS score, and randomization stratification category; all previous non-missing post-baseline NRS scores. Should convergence issues occur due to small cell size for the categorical covariates at either stage, they will be removed from the model.
- Results of the MMRM on the multiply imputed data sets will be summarized by the SAS MIANALYZE procedure.

Statistical Analysis Plan (SAP)

- The details of MNAR based imputation using SAS described under [Appendix H](#).

Descriptive statistics for the primary efficacy endpoint will also be provided by treatment group for each renal disease category (moderate CKD non-dialysis; severe CKD non-dialysis; severe CKD on dialysis). In addition, an analysis of the primary efficacy endpoint within each renal disease status will be performed using an MMRM model similar to the one implemented for the primary efficacy analysis but without renal disease status as a fixed effect. As the renal disease status was included a factor in the multiple missing data imputation for the primary analysis, the same multiple imputed datasets as created for the primary analysis and methods to combine results will be used for these analyses.

A linear trend test across the doses based on a MMRM model will also be presented to explore the dose response curve. The model will contain treatment as continuous variable (Placebo = 0 mg and other doses 0.25, 0.5, and 1.0 mg), week, and treatment-by-week interaction as fixed effects; baseline score and renal disease status as covariates. The estimate and p-value for overall effect of dose will be provided. An unstructured covariance matrix structure will be used to model the within patient errors.

Listings will be provided for Worst Itching Intensity NRS score for all the available visits.

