8.0 Statistical Methods

8.1 General Considerations

This protocol describes key safety and efficacy analyses of data collected as currently planned. A SAP will be developed based on the clinical protocol and eCRFs and finalized prior to unblinding of the study; it will include a detailed description of the statistical methodology including the treatment of missing data and the patient eligibility criteria. No database will be locked or analyses completed until the SAP has been approved. If differences occur between analyses of data described in the SAP and the current protocol, those found in the SAP will assume primacy.

Unless otherwise noted, continuous variables will be summarized using number of non-missing observations, mean, standard deviation, median, minimum, and maximum; categorical variables will be summarized using the frequency count and the percentage of patients in each category. In addition to the descriptive summaries, pertinent data listings will be provided.

All analyses will be performed using SAS[®] version 9.2 or higher, unless otherwise specified.

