8.6.3 Hypothesis Testing Strategy

Testing of the primary efficacy endpoint will be 2-sided and conducted at the 5% error level. The study will be considered positive if the null hypothesis of no treatment difference is rejected in favor of the alternative that patients randomized to CR845 experience significantly less itching as measured by the change from baseline to Week 12 of the Treatment Period with respect to the weekly mean of the 24-hour Worst Itching

Intensity NRS score. This is a Phase 2 study designed to identify a safe and efficacious dose; therefore, each CR845 dose group will be compared against placebo. There will be no adjustment for multiple comparison.

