5 SAMPLE SIZE AND POWER

The minimum total sample size for this study is $N = 240$ patients (60 per treatment group) and the maximum is $N = 480$ (120 per treatment group). An unblinded interim analysis (IA) will be conducted when approximately 50-60% of the planned 240 patients have been randomized and have either completed the 12-week Treatment period or have discontinued study drug early. The primary goal of the IA is to identify dose(s) of oral CR845 that are both safe and efficacious. Doses that are found to be unsafe or poorly tolerated will be dropped from the study. No dose will be dropped for futility reasons. The details of sample size re-estimation based on conditional power are described in [section 8.9.1](#). A sample size of 60 patients per treatment group (the minimum sample size) will provide adequate power ($\geq 80\%$) for effect sizes ≥ 0.52 for a 5% type 1 error and a 2-sided T-test. Assuming a standard deviation of 2.6 for the primary efficacy variable, an effect size of 0.52 corresponds to a difference of approximately 1.4 point on a 0- to 10-point scale.

A sample size of 120 patients per treatment group (the maximum sample size) will provide adequate power ($\geq 80\%$) for effect sizes ≥ 0.40 for a 5% type 1 error and a 2-sided T-test. Assuming a standard deviation of 2.6 for the primary efficacy variable, an effect size of 0.40 corresponds to a difference of approximately 1 point on a 0- to 10-point scale. The power of a 2-sided hypothesis test with a 5% Type 1 error as a function of sample size and effect size is presented below.

Power as a Function of Effect Size (N = 120 Per Arm)^a

Effect Size	0.55	0.52	0.50	0.45	0.40	0.35
Power (N = 120)	98%	97%	97%	93%	86%	77%
Power (N = 60)	84%	80%	77%	68%	58%	47%

^a Power for a 2-sided T-test with equal variance and a 5% Type 1 error.

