Unless otherwise stated, all statistical testing will be two-sided and will be performed using a significance (alpha) level of 0.05. Two-sided 95% confidence intervals (CI) will be provided appropriately. For tests of hypothesis of treatment group differences, the associated p-value will be reported. All p-values will be rounded to three decimal places; p-values that round to 0.000 will be presented as “< 0.001”.

All patients data, including those derived, will be presented in individual patient data listings. Unless otherwise stated, unscheduled visit results will be included in date/time chronological order, within patient listings only. All listings will be sorted by treatment, patient number, date/time and visit. Patient listings of efficacy and safety data will be presented for all full analysis set and safety set patients respectively unless specified otherwise.

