- Section 8.6.3 of the protocol stated that the study would be considered positive if the null hypothesis of no treatment difference is rejected in favor of the alternative that patients randomized to CR845 experience significantly less itching as measured by the change from baseline in the weekly mean of the Worst Itching Intensity score at Week 12. In fact, since this study compares several CR845 doses versus placebo, the study will be considered positive if at least one dose is found to be safe and effective. Effectiveness will be evaluated based on results of the primary efficacy analysis either using the estimate of treatment effect or the p-value of the hypothesis tests.

Statistical Analysis Plan (SAP)

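### The SAP's rule for a positive study accepts either the effect estimate or the p-value, with no cut for the estimate, so its false-positive rate cannot be stated in advance

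*SAP*

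**What the plan says.** Protocol 8.6.3 sets a test-based criterion: "The study will be considered positive if the null hypothesis of no treatment difference is rejected in favor of the alternative" that CR845 patients itch less, at the two-sided 5% level.

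SAP 8.6.2 replaces it. The study is positive if at least one safe and efficacious dose is identified, and effectiveness is "evaluated based on results of the primary efficacy analysis either using the estimate of treatment effect or the p-value of the hypothesis tests". SAP Section 9 declares this as a change from the protocol: because several doses are compared with placebo, "the study will be considered positive if at least one dose is found to be safe and effective". Protocol 8.1 settles which text governs where the two differ: "those found in the SAP will assume primacy".

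The surrounding provisions are:

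- SAP 8.1: "all statistical testing will be two-sided and will be performed using a significance (alpha) level of 0.05".
- SAP 8.6.1.1: "There will be no adjustment for multiple comparisons".
- SAP 8.6.2 tests three dose-specific null hypotheses (H01 to H03) and a pooled one (H04). Of the pooled comparison it says: "The treatment difference between all doses combined and placebo will be estimated using a similar approach".
- SAP 5 gives planning differences. At 60 per arm, "an effect size of 0.52 corresponds to a difference of approximately 1.4 point on a 0- to 10-point scale"; at 120 per arm, an effect size of 0.40 corresponds to about 1 point.

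**The concern.** A success rule should say which result leads to which verdict. Here the 5% level governs only the p-value. The estimate has no threshold, and nothing says whether it stands beside the p-value or in place of it. The results that SAP 8.6.2 lists for presentation carry no decision cut, and the differences in SAP 5 are power assumptions not linked to the rule. The type 1 error statement in SAP 8.9.1 concerns the interim sample-size rule. The reason given in Section 9, that there are several doses, explains the move to at least one dose. It does not explain the estimate route.

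The sentence can be read in two ways:

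- **Reading A:** either measure suffices. A study with no significant dose can be positive.
- **Reading B:** one measure is picked as the yardstick. If it is the estimate, a significant dose can fail.

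At stake is the study-level conclusion. For an inert drug, the chance of a positive verdict depends on a cut and a reading that could both be chosen after the data are seen.

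**Working it through.** **Inputs.** SD 2.6 (SAP 5); 60 per arm planned, up to 120 (SAP 5); 1:1:1:1 allocation with a shared placebo (SAP 3.2); two-sided 5% per test, unadjusted (SAP 8.1, 8.6.1.1). Cuts on the estimate are assumptions, because the documents give none for this rule. Arm means are taken as normal and the safety condition is not modelled.

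**The plan's own power figures.** A noncentral-t calculation gives 80.6% at 60 per arm and effect size 0.52 (stated 80%), and 87.0% at 120 per arm and 0.40 (stated 86%). The planning basis is reproduced to within about a point.

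**Significance boundary.** The SE of a dose-placebo difference is 2.6 × √(2/n).

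- n = 60: SE = 0.4747; 1.96 × SE = 0.930 point.
- n = 120: SE = 0.3357; 1.96 × SE = 0.658 point.

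**Chance under an inert drug that at least one of three doses beats placebo by c or more:**

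P(c) = 1 − ∫ φ(z) · Φ(c / (2.6/√n) + z)³ dz

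Reading A uses the smaller of c and the boundary. Reading B, with the estimate as yardstick, uses c itself.

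| Assumed cut (points) | A, n = 60 | of which no dose significant | A, n = 120 | B, n = 60 | B, n = 120 |
|---|---|---|---|---|---|
| 0 | 75% | 69% | 75% | 75% | 75% |
| 0.25 | 53% | 47% | 43% | 53% | 43% |
| 0.5 | 30% | 24% | 16% | 30% | 16% |
| 0.75 | 13% | 7.1% | 6.3% | 13% | 3.3% |
| 1.0 | 6.3% | 0 | 6.3% | 4.5% | 0.41% |
| 1.4 | 6.3% | 0 | 6.3% | 0.45% | below 0.01% |

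The p-value route alone gives 6.3% at either sample size. Under reading A the estimate adds nothing once the cut reaches 0.93 point at 60 per arm, or 0.66 at 120 per arm.

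**Reading B can lose a real effect.** At 120 per arm and a true difference of 1.0 point, for one dose:

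- P(significant) = 1 − Φ((0.658 − 1.0)/0.3357) = 0.846.
- P(significant but estimate below 1.0) = Φ(0) − Φ((0.658 − 1.0)/0.3357) = 0.500 − 0.154 = 0.346.

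**Pooled test.** With SE 2.6 × √(1/n + 1/(3n)), counting H04 as a further p-value route moves 6.3% to 6.5% (4 million simulated trials, n = 60).

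**With the SAP 8.9.1 re-estimation.** One million simulated trials, interim at 30 per arm, and the new size taken as the smallest n from 60 to 120 reaching 80% conditional power. Reading A gives 74%, 49%, 25%, 11% and 6.4% at cuts of 0, 0.25, 0.5, 0.75 and 1.0 point. Reading B gives 3.3% at 1.0. An interim at 36 per arm changes none of these by more than about half a percentage point.

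**The case against.** The strongest reply has four parts.

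**Phase 2 purpose.** The study is meant to find a dose, both documents decline multiplicity adjustment, and study-level error was never held at 5%. Weighing effect size beside the p-value is a legitimate aim in dose selection. This stands as far as it goes. It defends using an estimate, but not using one without a criterion.

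**Limited reach.** Endpoint, model, contrast, hypotheses and test level are all fixed, the change is openly declared, and every estimate, interval and p-value will be reported. A reader would see that no dose was significant. This also stands, and it is why the point concerns the verdict and not the estimates. Declaring an undefined rule does not define it.

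**The large figures rest on assumed cuts.** The only differences the plan mentions, about 1.0 and 1.4 points, add nothing under reading A and lower the error under reading B. The 75% case is an extreme that the text does not state. This is fair. The figures show how far the rate can move, not an expected inflation, and the unmodelled safety condition can only lower them.

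**H04.** The rule speaks of identifying a dose, and a pooled test identifies none. That largely answers the question. Because H04 is listed among the tested hypotheses, a clarifying clause is still worth adding, though its effect is small.

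It can also be argued that stating a cut, and whether it joins the p-value by 'and' or 'or', would be enough without removing the estimate route. That would make the error rate statable. It would not restore the protocol's criterion, and Section 9 gives no reason for departing from that part of it.

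**Conclusion.** The concern holds. Following the SAP as written, a study with no significant dose can be called positive, and the governing text contains nothing that limits how often. At 60 per arm the chance that an inert drug meets the efficacy part runs from 6.3% to 75% under reading A, depending on the unstated cut. Under reading B it can be as low as 0.45% at a 1.4-point cut. Reading B can also work against the drug: at 120 per arm and a true 1.0-point difference, 35% of trials would have a significant dose that misses a 1.0-point cut.

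These figures assume normal arm means and SD 2.6, and leave the safety judgement out. The defect itself does not depend on them. It should be fixed before final unblinding, although the reported estimates and tests are unaffected.

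**What to change.** In SAP 8.6.2 and Section 9, remove the words that offer the estimate as an alternative to the p-value, and write:

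> The study is positive if at least one CR845 dose is judged safe and, for that dose, H01, H02 or H03 is rejected at the two-sided 5% level (unadjusted across doses) with the Week 12 LS mean difference favouring CR845. The pooled H04, the estimates and the 95% CIs are supportive.

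If an estimate-based criterion is wanted for choosing a dose, state its numerical threshold before final unblinding and label it separately from the positive-study verdict.

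The cost is two sentences, with no effect on patients or procedures. The documents do not show whether the unblinded interim analysis has taken place, so staff without access to interim results should make the edit. The sponsor gives up the option of calling a non-significant study positive. An error of about 6.3% in the favourable direction remains across three unadjusted doses, which follows from the plan's decision on multiplicity. The safety judgement stays as the SAP has it.

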3.2 Randomization and blinding

Before the start of the study, a computer-generated randomization schedule will be prepared. Randomization will be performed using an interactive voice or web response system (IVRS/IWRS). Patients will be randomized in a 1:1:1:1 ratio to receive either placebo or CR845 tablets at doses of 0.25, 0.5, or 1 mg. Randomization will be stratified according to the patient's renal disease status: moderate CKD non-dialysis; severe CKD non-dialysis; severe CKD on dialysis (ie, 3 categories). The randomization of severe CKD patients on hemodialysis will be capped at approximately 20% of the total sample size (ie, 48 of 240 patients).

Patients, investigators, study staff, and the sponsor will be blinded to study drug assignment. For medically urgent or emergent situations that necessitate knowledge of study drug assignment for patient management, the blind may be broken via the IVRS/IWRS. Whenever possible, the medical monitor should be contacted prior to breaking the blind. The sponsor and medical monitor will receive a report whenever a patient blind is broken.

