8.6.3 Analysis of secondary efficacy endpoint(s)

The key secondary efficacy endpoints are:

- Change from baseline in itch-related quality of life at the end of Week 12, as assessed by the total Skindex-10 scale score;
- Change from baseline in itch-related quality of life at the end of Week 12, as assessed by the total 5-D Itch scale score;
- Proportion of patients achieving an improvement from baseline ≥ 3 points with respect to the weekly mean of the daily 24-hour Worst Itching Intensity NRS score at Week 12 of the Treatment period.

The Skindex-10 scale total score and the 5-D Itch total scale score will be analyzed using MMRM that will contain treatment, week, and treatment-by-week interaction as fixed effects; baseline score and renal disease status as covariates. Repeated measures will include values that reflect the Skindex-10 and 5-D total score at the end of weeks 4, 8, 10, and 12. The total score derivation for Skindex-10 and 5-D Itch scale detailed in [Appendix B](#) and [Appendix C](#) respectively.

The baseline value will be defined as the value of the Skindex-10 or 5-D Itch total score collected on Day 1 prior to randomization. Missing Skindex-10 Itch scale and 5-D Itch scale

Statistical Analysis Plan (SAP)

total scores will be imputed in a similar fashion as the primary endpoint for the MMRM analyses using the MI approach assuming data is missing at random. The mean treatment difference between each CR845 dose and placebo, and between all CR845 doses combined and placebo will be estimated as the simple contrast in the treatment effect at Treatment period week 12.

Descriptive statistics will be provided for the observed value and change from baseline at week 12 by treatment group for Skindex-10 scale and the 5-D Itch total scores. The adjusted LS means and SE from the model will be presented for each treatment group. The LS means estimate for the difference, standard error, 95% CI, and p-value will be presented. The analysis will be conducted using the Full Analysis Set.

An unstructured covariance matrix structure will be used to model the within patient errors. If there are convergence issues, other structures that require fewer parameters will be applied in the following order: 1) heterogeneous Toeplitz, 2) autoregressive, 3) compound symmetry until convergence is attained. The Kenward-Roger approximation will be used to estimate the denominator degrees of freedom.

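### The MMRMs impose one baseline slope on every week; prespecifying baseline-by-week would protect the precision of the Week 12 contrast at negligible cost

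*SAP*

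**What the plan says.** SAP 8.6.2 defines the primary MMRM: "The model will contain treatment, week, and treatment-by-week interaction as fixed effects; baseline score and renal disease status as covariates". Protocol 8.6.1 lists the same terms and adds a patient random effect. Neither includes an interaction of baseline with week. The estimate of interest comes from one week only: "the treatment group difference vs placebo will be estimated as the simple contrast in the treatment effect at Week 12 of the Treatment Period".

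SAP 8.6.3 uses the same structure for the Skindex-10 and 5-D totals at Weeks 4, 8, 10 and 12, again with "baseline score and renal disease status as covariates".

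Three other features of SAP 8.6.2 matter here:

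- The within-patient covariance is unstructured, with simpler structures only if the model fails to converge.
- Missing weekly scores are imputed before the primary analysis. The monotone regression uses baseline and all earlier weeks, so baseline has its own coefficient at each week.
- Sensitivity analysis 1 fits the same MMRM without imputation and states that the treatment differences are unbiased if data are MAR.

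**The concern.** A change score can depend on baseline differently at Week 1 and at Week 12. If it does, a common slope is a compromise, and the compromise is not an even one. With an unstructured covariance the fit gives most weight to weeks with small variance. If the spread of change scores grows over the Treatment Period, those are the early weeks. The pooled slope can then sit near the Week 1 slope, or even beyond it, and Week 12 is under-adjusted for baseline. The cost is precision in the one contrast that decides the primary result.

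Sensitivity analysis 1 raises a second issue. Without imputation, the MMRM's mean model carries the whole MAR argument. If dropout depends on baseline, and does so differently by arm, a wrong common slope can shift the Week 12 contrast.

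**Working it through.** **The plan's own figure.** SAP 5 claims at least 80% power "for effect sizes ≥ 0.52 for a 5% type 1 error and a 2-sided T-test" with 60 per arm. The noncentral t gives 80.7%. For 120 per arm at effect size 0.40 it gives 87.0% against the stated 86%. All 12 cells of the power table reproduce within 2 points. The design difference is 0.52 × 2.6 = 1.352.

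**Inputs from the documents.** 60 per arm, 240 in total, two-sided 5%. The SD of 2.6 (SAP 5) is taken as the raw SD of the Week 12 change.

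**Assumed inputs.** The documents give none of these:

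- Baseline SD 1.2-1.6. Entry restricts baseline to 5-10, where a uniform spread has SD 1.44.
- SD of change rising from 1.3 at Week 1 to 2.6 at Week 12.
- Within-patient correlation AR 0.9 or compound symmetry (CS) 0.7.
- Baseline slope constant at −0.3, in moderate drift (−0.2 to −0.4, or −0.1 to −0.4), or in steep drift (−0.1 to −0.6).
- Complete data.

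**Formulas.** Let β be the vector of weekly slopes and S the residual covariance.

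- Pooled slope: b = 1′S⁻¹β / 1′S⁻¹1.
- Week 12 residual variance: s² = 2.6² − β₁₂² × SD_base².
- SE with common slope: √(2[s² + (β₁₂ − b)² SD_base²]/60).
- SE with baseline-by-week: √(2s²[1 + 1/236]/60), where 236 = 240 − 4.

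**One case in full** (−0.1 to −0.4, AR, baseline SD 1.4). The pooled slope is −0.134, so the Week 12 gap is 0.266. Then s² = 6.76 − 0.16 × 1.96 = 6.4464, and the misfit adds 0.266² × 1.96 = 0.1387. The common-slope SE is √(2 × 6.5851/60) = 0.4685. With the term it is √(2 × 6.4464 × 1.00424/60) = 0.4645. The common-slope SE is 0.9% wider.

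**Results at baseline SD 1.4:**

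| True slope, Week 1 to 12 | Correlation | Pooled slope | SE, common | SE, by week | Power, common → by week |
|---|---|---|---|---|---|
| −0.3 constant | either | −0.300 | 0.4685 | 0.4694 | 81.7% → 81.5% |
| −0.2 to −0.4 | AR | −0.221 | 0.4658 | 0.4645 | 82.1% → 82.3% |
| −0.2 to −0.4 | CS | −0.119 | 0.4691 | 0.4645 | 81.6% → 82.3% |
| −0.1 to −0.4 | AR | −0.134 | 0.4685 | 0.4645 | 81.7% → 82.3% |
| −0.1 to −0.4 | CS | 0.023 | 0.4760 | 0.4645 | 80.4% → 82.3% |
| −0.1 to −0.6 | AR | −0.163 | 0.4629 | 0.4502 | 82.6% → 84.6% |
| −0.1 to −0.6 | CS | 0.106 | 0.4841 | 0.4502 | 79.1% → 84.6% |

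**Ends of the range over baseline SD 1.2-1.6**, as the ratio of common-slope SE to by-week SE:

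- Moderate, smallest (SD 1.2, −0.2 to −0.4, AR): s² = 6.5296, misfit 0.179² × 1.44 = 0.0461, ratio √(6.5757/6.5573) = 1.001.
- Moderate, largest (SD 1.6, −0.1 to −0.4, CS): s² = 6.3504, misfit 0.423² × 2.56 = 0.4581, ratio √(6.8085/6.3773) = 1.033.
- Steep, smallest (SD 1.2, AR, pooled slope −0.160): s² = 6.2416, misfit 0.440² × 1.44 = 0.2788, ratio √(6.5204/6.2681) = 1.020.
- Steep, largest (SD 1.6, CS): s² = 5.8384, misfit 0.706² × 2.56 = 1.2760, ratio √(7.1144/5.8631) = 1.102.

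**Simulation check** (3,000 trials per scenario, four arms of 60, unstructured covariance, baseline SD 1.4). Mean model SE, common against by-week, was 0.4677 against 0.4687 (constant, AR), 0.4680 against 0.4642 (−0.1 to −0.4, AR) and 0.4845 against 0.4505 (−0.1 to −0.6, CS). Bias of the Week 12 contrast was 0.013 or less under both models in every scenario run.

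**Sensitivity analysis 1.** A further simulation assumed MAR dropout of about 27% on active and 16% on placebo, depending on baseline, with baseline SD 1.4. The two models' Week 12 contrasts differed by about 0.04-0.12 NRS points when dropout ran with baseline in opposite directions by arm. The difference was 0.02-0.08 when only one arm's dropout depended on baseline, and 0.01-0.03 when both arms behaved alike. The first range is 3-9% of 1.352. These sizes move with the assumed strength of the dropout relation.

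**The case against.** The strongest reply is that nothing in the documents shows a drifting slope. There are no weekly slopes, no baseline SD and no correlations. With a constant slope the added term makes the SE 0.2% wider. That stands, and it makes the gain conditional. The possible loss is still far smaller than the possible gain.

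The power calculation is an unadjusted t-test that credits nothing to baseline adjustment, so the planned power does not depend on this choice. That also stands.

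Three stronger readings are tempting, and the documents do not support them:

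- A reader might infer that the primary contrast is biased or its SE wrong. Randomisation keeps the complete-data contrast unbiased, and the unstructured residual covariance absorbs the misfit.
- A reader might infer that the mismatch between imputation and analysis models is a fault. An imputation model richer than the analysis model is not a defect; imputed Week 12 values simply do not carry the common-slope constraint.
- A reader might infer that the term is free. It adds parameters, and the within-stratum MMRMs would probably inherit it. The dialysis stratum is capped at about 48 of 240 patients, or roughly 12 per arm, with 12 weeks and an unstructured matrix, so convergence could suffer.

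The text of the SAS appendices from F onward is blacked out, so the coded model cannot be checked. The point rests on the model as written.

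**Conclusion.** The point holds as a low-priority efficiency improvement. As written, one baseline slope is imposed on all weeks while the contrast is taken at Week 12. Under the assumed values the common slope costs about 0.1-3% in SE for moderate drift and 2-10% for steep drift; under a constant slope it saves about 0.2%. The upper figures need steep drift, compound-symmetric correlation and a wide baseline spread together. No dropout or imputation variance enters these figures, and none was computed for Skindex-10 or 5-D.

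For sensitivity analysis 1, the statement of unbiasedness under MAR is incomplete, because it also requires a correct mean model. Under the dropout assumed, the effect was modest and was largest when dropout depended on baseline differently by arm.

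**What to change.** Prespecify baseline-by-week as a fixed effect in the NRS MMRM, including sensitivity analysis 1, and baseline-by-visit in the Skindex-10 and 5-D MMRMs. Compute least-squares means at the overall mean baseline. Record the change in SAP section 9, since the protocol lists the model without the term. Allow the term to be dropped from the within-stratum models if they do not converge. The same single-effect restriction applies to renal disease status, and the team may wish to state whether that is intended.

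The cost is 11 extra parameters for the NRS (12 weekly slopes in place of one) and 3 for each questionnaire (four visits), with a negligible loss of precision if the slope is in fact constant. No new data are needed.
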